#### 4.3.3. Supplementary analyses

#### 4.3.3.1. Analysis Related to the Treatment Regimen Estimand

The analysis related to the "treatment-regimen" estimand will be conducted using data in the FAS.

The analysis for the mean percent change in body weight will be conducted utilizing ANCOVA. The response variable for the ANCOVA model will be percent change in body weight from randomization to Week 72. This model will include terms of baseline IGT (yes or no); baseline hyperlipidemia (based on TG; yes or no); baseline NAFLD (yes or no) and sex (female, male) as fixed effects and baseline body weight as a covariate. The ANCOVA analysis will be conducted with multiple imputation of missing body weight at Week 72 and statistical inference over multiple imputation of missing data guided by Rubin (1987).

With the aid of the ANCOVA model, 2-sided 95% CI for mean change in percent body weight from baseline to the 72-week visit between tirzepatide 10 mg or 15 mg QW and placebo will be derived.

With the aid of the logistic regression model, 2-sided 95% CI and odds ratio for percentage of participants achieving at least 5% body weight reduction from baseline to the 72-week visit between tirzepatide 10 mg or 15 mg QW and placebo will be derived.

#### 4.3.3.2. Methods for Multiple Imputations

For efficacy analyses relative to the "treatment-regimen" estimand, the intercurrent events (ICEs) and the resulting missing values will be handled as follows:

- Category 1: for missing data solely due to an exceptional circumstances, such as a pandemic or natural disaster (after other reasons for missing data are ruled out), considers the missing data as missing at random. The missing data will be imputed using all nonmissing data of the primary outcome measurement from the same treatment arm.
- Category 2: for missing data due to all other reasons, it will be imputed based on retrieved dropouts in the same treatment arm, defined as observed primary outcome measurements, from participants in the same treatment group who had their efficacy assessed after early discontinuation of study drug. In cases where there are not enough retrieved dropouts to provide a reliable imputation model (for example, the model implemented by the SAS program does not converge), an alternative multiple imputation method with reference to the placebo group (that is, placebo multiple imputation) will be used.

### 4.4. Secondary Endpoint Analysis

#### 4.4.1. Definition of endpoints

#### 4.4.1.1. Definition of body mass related parameters

Body mass index (kg/m²) will be derived using body weight in kilograms divided by the square height in meters.

Excess weight loss (%) will be derived using [(initial weight) – (current weight)]/[(initial weight) – (ideal weight)] x 100), with ideal weight considered as the weight corresponding to a BMI = 22 kg/m^2.

#### 4.4.1.2. Defined Obesity-Related Health Problems

The definition of baseline obesity-related health problems (ORHPs) are:

- IGT from 2-hour OGTT results: Fasting glucose or 0-hour OGTT = 110-125 mg/dL (6.1-6.9 mmol/L) and/or 2-hour OGTT = 140-199 mg/dL (7.8-11.0 mmol/L).
- **Hyperlipidemia**: triglyceride (TG) ≥150 mg/dL at baseline
- NAFLD: HFF  $\geq$ 5% by MRI at baseline

Definition of IGT is based on the GPHZ protocol (b). For each subjects, baseline ORHPs are determined by the measurements (not by the inputs of IWRS).

The definition of improvements of each defined obesity-related health problems are:

- **IGT** (only for participants with IGT at baseline)
  - o Return to normal blood glucose range
    - OGTT 0-hour glucose <110 mg/dL AND

- OGTT 2-hour glucose <140 mg/dL
- **Hyperlipidemia** (only for participants with hyper-triglyceridemia [triglyceride (TG) ≥150 mg/dL] at baseline)
  - o Return to normal range (TG <150 mg/dL) OR
  - o Reduced by 30% from baseline
- NAFLD (only for participants with diagnosis of NAFLD [HFF ≥5%] by MRI at baseline)
  - o Return to normal range (HFF <5%) OR
  - o Reduced by 30% from baseline

Incident diabetes is followed by Japanese Clinical Practice Guideline for Diabetes 2019 (Araki et al. 2020) and defined when any 1 of the following occur after randomization:

- unequivocal hyperglycemia (random glucose ≥200 mg/dL) with signs or symptoms of hyperglycemia (e.g., dry mouth, polyposia, polyuria, body weight loss, or diabetic retinopathy).
- within a 4 week period, the following laboratory evidence of diabetic type criteria including either HbA1c ≥6.5%, or glucose levels (fasting glucose or OGTT 0 hour glucose ≥126 mg/dL and/or OGTT 2 hour glucose ≥200 mg/dL) are observed:
  - o Both glucose level and HbA1c meets diabetic type criteria
  - o Only glucose level meets diabetic type criteria
    - With typical symptoms of DM or definite diabetic retinopathy
    - Without typical symptoms of DM or definite diabetic retinopathy, re-exam within 1 month and:
      - Both glucose level and HbA1c meets diabetic type criteria
      - Only glucose level meets diabetic type criteria
      - Only HbA1c meets diabetic type criteria
  - o Only HbA1c meets diabetic type criteria, re exam within 1 month and
    - Both glucose level and HbA1c meet diabetic type criteria
    - Only glucose level meets diabetic type criteria
- initiation of any medication for the treatment of diabetes

#### 4.4.1.3. Definition of composites of improvements of Obesity-Related Health Problems

Regarding the following endpoint in the secondary endpoint, definition of response is described below.

Proportion of participants who met the following criteria at 72 weeks from BL

- Improvement in at least 2 obesity related health problems for participants with BL BMI >27 and <35 kg/m², or
- Improvement in at least 1 obesity related health problem for participants with BL BMI >35 kg/m^2

#### Responder is defined as:

- Post-baseline number of ORHP is 1 or 0 for participants with BL BMI >27 and <35 kg/m^2
- Post-baseline number of ORHP is 0 for participants with BL BMI >35 kg/m^2

#### 4.4.1.4. Definition of IGT related parameters

Homeostatic Model Assessment for Beta Cell and Insulin Sensitivity (HOMA2 %B and HOMA2 %S): Fasting glucose and insulin values will be used to calculate beta-cell function and insulin sensitivity using the updated Homeostasis Model Assessment (HOMA2) (Wallace et al. 2004).

#### 4.4.1.5. Definition of parameters related to 2-hour OGTT

The following parameters will be collected during 2-hour OGTT for each scheduled OGTT visit:

- glucose
- insulin, and
- C-peptide.

For each above parameter, the mean concentration over 120 minutes plots will be created by glycemia status at randomization and by treatment group and by OGTT visit (that is, at baseline and at Week 72).

For each above parameter, the area under the curve from time zero to 2 hours  $(AUC)_{(0-2h)}$  during OGTT will be calculated using the trapezoidal rule. The respective  $AUC_{(0-2h)}$  will be summarized by treatment group and by OGTT visit.

In addition, the following OGTT derived parameters (Araki et al. 2020) will be calculated at each OGTT visit for each participant with OGTT:

- Glycemic response categories:
  - o Normal:
    - OGTT 0 hour glucose <110 mg/dL AND
    - OGTT 2-hour glucose <140 mg/dL

  - Borderline type:
    - OGTT 0 hour glucose =110-125 mg/dL (6.1-6.9 mmol/L) **OR**
    - OGTT 2-hour glucose =140-199 mg/dL (7.8-11.0 mmol/L)
  - o Suspected T2DM:
    - o OGTT 0 hour glucose ≥126 mg/dL AND
    - o OGTT 2-hour glucose ≥200 mg/dL
- Matsuda Index =  $\frac{10000}{\sqrt{(FPG \times FPI) \times (\bar{G} \times \bar{I})}}$ , where FPG is the fasting glucose, FPI is the fasting insulin,  $\bar{G}$  denotes the mean glucose during OGTT, and  $\bar{I}$  denotes the mean insulin during OGTT

- Insulin secretion =  $\left(\frac{\Delta C_{\text{pep}}}{\Delta G}\right)_{0-120}$ , where  $\Delta C_{\text{pep}}$  denotes the incremental area under the plasma C-peptide curve during the 2-hour OGTT, and  $\Delta G$  denotes the incremental area under the plasma glucose concentration curve during 2-hour OGTT
  - O Insulin secretion index =  $\frac{\left(\frac{\Delta C_{pep}}{\Delta G}\right)_{0-120}}{normal\ level\ of\ insulin\ secretion}$ , where normal level of insulin secretion is the median value for insulin secretion, ie,  $\left(\frac{\Delta C_{pep}}{\Delta G}\right)_{0-120}$ , in participants with normal glucose tolerance at baseline
  - o Normal insulin secretion: insulin secretion index >70%
  - Moderate impairment of insulin secretion: 50% to 70% (inclusive) of the insulin secretion index
  - o Severe impairment of insulin secretion: <50% of the insulin secretion index
- $\beta$ -cell function = Insulin secretion \* Matsuda index =  $\left(\frac{\Delta C_{\text{pep}}}{\Delta G}\right)_{0-120}$  \*  $\frac{10000}{\sqrt{(FPG \times FPI) \times (\bar{G} \times \bar{I})}}$

## 4.4.2. Main analytical approach

# **4.4.2.1.** Main Analytical Approach for Continuous Measures with Only 1 Postbaseline Measure

For mean change from randomization or actual measurement at 72 week visit, an ANCOVA model will be used.

An ANCOVA model with terms of treatment group, stratification factors: baseline IGT (yes or no); baseline hyperlipidemia (based on TG; yes or no); baseline NAFLD (yes or no) and sex (female, male) as fixed effects, baseline measurement as a covariate.

For measurement with only 1 postbaseline measure during the analysis period per schedule of activity, where LOCF approach will be applied to impute the endpoint when ED measure is available.

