9.4.3. Efficacy Analyses

9.4.3.1. Primary Analyses

The primary efficacy analysis will be guided by the "efficacy" estimand, which represents efficacy prior to discontinuation of study drug under missing at random assumption. The efficacy analyses will be conducted using the EAS. The primary analysis model will be a MMRM for body weight percentage change over time and longitudinal logistic regression for proportion of participants achieving at least 5% body weight reduction over time. The response variable of MMRM will be the percent change in body weight from baseline values obtained at each scheduled postbaseline visit. The response variable of longitudinal logistic regression will be the achievement of at least 5% body weight reduction at each scheduled postbaseline visit. The independent variables of both analysis models are treatment group (tirzepatide 10 mg, tirzepatide 15 mg, and placebo), visit, and treatment by visit interaction, stratification factors: baseline IGT (yes or no); baseline hyperlipidemia (based on TG; yes or no); baseline NAFLD (yes or no) and sex (female, male), and baseline body weight as a covariate. An unstructured covariance structure will model relationship of within-patient errors. The Kenward-Roger approximation will be used to estimate denominator degrees of freedom. Since the mean percent change in body weight and the percentage of participants with $\geq 5\%$ body weight reduction needs to be achieved at the same time, no multiplicity adjustment is planned for these 2 tests.

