#### 1.1.2.1. Primary estimand

The estimand is described by the following attributes:

- Population: all randomized participants who received at least 1 dose of treatment.
- Endpoint: mean percent change from randomization to Week 72 in body weight, AND percentage of study participants who achieve ≥5% body weight reduction from randomization to Week 72.
- Treatment condition of interest: tirzepatide 10 mg and/or 15 mg QW vs. placebo, excluding data after discontinuation of study drug. Temporary interruptions and modification prior to discontinuation will be allowed as part of the treatment conditions.
- Handling of intercurrent events: the intercurrent events of treatment discontinuation for any reason is addressed by the treatment condition of interest attribute and handled by the hypothetical strategy.
- Population-level summary: difference in mean percent changes between treatment conditions, AND difference in response percentage between treatment conditions.

Rationale for estimand: the estimand aims to reflect treatment efficacy in an envisaged scenario in which the intercurrent events leading to treatment discontinuation would not occur.

This estimand is referred to as 'efficacy' estimand in the latter of this document.

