Analysis Dataset	Analysis Type	Baseline	Postbaseline
SS	1.1) Treatment-Emergent Adverse Events	The baseline period is defined as the start of screening and ends prior to the first dose in of study treatment (typically at Week 0).	Starts after the first dose of study treatment and ends at the end of the study period (including off-drug follow up visit).
SS	1.2) Treatment-Emergent Abnormal Labs a , Vital Signs, and ECGs.	Baseline will include all scheduled and unscheduled measurements during the baseline period (Visit 1 to Visit 3)	Postbaseline will be defined as above (1.1). All scheduled and unscheduled measurements will be included.
SS	1.3) Change from Last Baseline to Week xx and to Last Postbaseline for Labs a ,Vital Signs, and ECGs.	The last scheduled and unscheduled non-missing assessment recorded during the baseline period defined above (1.2).	Postbaseline will be defined as above (1.1). Only scheduled visits will be included. The early discontinuation (ED) visits are considered scheduled visits.

Table GPHZ.4.1. Baseline and Postbaseline Definitions for Safety Analysis

Abbreviations: ECGs = electrocardiogram; SS = Safety Analysis Set.

For the primary and secondary efficacy endpoint analyses, data for participants with missing values at the 72-week visit will be imputed based on the method described in Section 4.3.2. Otherwise, missing values will not be explicitly imputed except for the parameters with only 1 postbaseline measure during the analysis period per schedule of activity, where last observation carried forward (LOCF) approach will be applied to impute the endpoint when ED measure is available.

End of study participation for a participant will be the earliest of date of death, date of withdrawal from further participation in the study, or date of safety follow-up visit (Visit 801). For participants considered to be lost-to-follow-up, end of study participation will be the date of lost-to-follow-up reported by the investigator. Participant data included in the database after the last date of study participation (including safety follow-up period) will be excluded from statistical analysis.

Statistical treatment comparisons will only be performed between tirzepatide 10 mg or 15 mg, and placebo. Since the trial is not adequately powered to detect difference among tirzepatide doses, comparisons among tirzepatide doses will not be performed unless otherwise specified.

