## 4.4.3. Secondary and Exploratory Endpoints

Table GPHZ.4.2. Secondary and Exploratory Efficacy Measures for Improvement of Obesity-related Health Problems

Analysis variable	Criteria/Measures	Analysis set	Analysis method	Additional Information
Percentage of participants who met the following criteria at 72 weeks from BL	Improvement in at least 2 obesity related health problems for participants with BL BMI >27 and <35 kg/ m², or Improvement in at least 1 obesity related health problem for participants with BL BMI >35 kg/ m²	Efficacy analysis set	Logistic model in Section 4.4.2.2	Definition of endpoint: 4.4.1.3
	Improvement in at least 2 obesity-related health problems	Efficacy analysis set - participants with BL BMI ≥27 and <35 kg/m²	Logistic model in Section 4.4.2.2	Exploratory
	Improvement in at least 1 obesity-related health problem	Efficacy analysis set - participants with BL BMI ≥35 kg/m 	Logistic model in Section 4.4.2.2	Exploratory
Improvement in laboratory tests for obesity-related health problems (72 weeks)	Mean changes in OGTT 2-hr glucose at 72 weeks from BL	Efficacy analysis set - participants with IGT at BL	MMRM model in Section 4.3.2.1	
	Mean changes in fasting glucose at 72 weeks from BL	Efficacy analysis set - participants with IGT at BL	MMRM model in Section 4.3.2.1	
	Mean changes in Fasting lipids (TG) at 72 weeks from BL	Efficacy analysis set - participants with hyperlipidemia at BL	MMRM model in Section 4.3.2.1	
	Mean changes in HFF at 72 weeks from BL	Efficacy analysis set - participants diagnosed as NAFLD by MRI at BL	ANCOVA model in Section 4.4.2.1	
Improvement of IGT (72 weeks)	Proportion of participants who achieved improvements of IGT	Efficacy analysis set - participants with IGT at BL	Logistic model in Section 4.3.2.2	

Analysis variable	Criteria/Measures	Analysis set	Analysis method	Additional Information
Improvement of hyperlipidemia (72 weeks)	Proportion of participants who achieved improvements of hyperlipidemia	Efficacy analysis set - participants with hyperlipidemia at BL	Longitudinal logistic model in Section 4.4.2.3	
Improvement of NAFLD (72 weeks)	Proportion of participants who achieved improvements of NAFLD	Efficacy analysis set - participants diagnosed as NAFLD by MRI at BL	Logistic model in Section 4.3.2.2	Compare TZP 10 mg, 15 mg and pooled TZP doses with placebo

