Abbreviations: ALT = alanine aminotransferase; AST = aspartate aminotransferase; BL = baseline; eGFR = estimated glomerular filtration rate; ELF = enhanced liver fibrosis; FFA = free fatty acid; FIB-4 = Fibrosis-4; GGT = gamma-glutamyl transferase; HbA1c = glycated hemoglobin; HDL-C = high-density lipoprotein cholesterol; HOMA2-%B = homeostasis model assessment estimates steady state beta cell function; HOMA2-%S = homeostasis model assessment estimates steady state insulin sensitivity; hs-CRP = high-sensitivity C-reactive protein; IGT = impaired glucose tolerance; K-18 (M30) = keratin-18 M30 fragment; LDL-C = low-density lipoprotein cholesterol; MMRM = mixed model for repeated measures; NAFLD = non-alcoholic fatty liver disease; Pro-C3 = a fragment of the NH2-terminal propeptide of type III procollagen; T2DM = type 2 diabetes mellitus; TC = total cholesterol; TG = triglycerides; TNFα = tumor necrosis factor alpha; TZP = tirzepatide; UACR = urine albumin-to-creatinine ratio; VLDL = very low-density lipoproteins.

Unless otherwise stated, the assessment of secondary efficacy objective will be guided by the "efficacy" estimand, using the same population as for primary analysis.

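### Carrying the early-discontinuation value forward to Week 72 does not estimate the efficacy estimand assigned to the secondary endpoints; patient-reported outcomes are the most exposed

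*SAP*

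**What the plan says.** **Estimand.** SAP 4.4.3 states "Unless otherwise stated, the assessment of secondary efficacy objective will be guided by the" efficacy estimand. SAP 1.1.2.1 handles discontinuation by the hypothetical strategy and describes the target as "treatment efficacy in an envisaged scenario in which the intercurrent events leading to treatment discontinuation would not occur". Protocol 9.4.3.1 says that this estimand "represents efficacy prior to discontinuation of study drug under missing at random assumption".

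**Missing-data rule.** SAP 4.1 first says that, for primary and secondary endpoints, "data for participants with missing values at the 72-week visit will be imputed based on the method described in Section 4.3.2". It then says that missing values are otherwise not imputed, except for parameters with one post-baseline measure, "where last observation carried forward (LOCF) approach will be applied to impute the endpoint when ED measure is available". SAP 4.4.2.1 (continuous) and 4.4.2.2 (binary) repeat the LOCF rule: "where LOCF approach will be applied to impute the endpoint when ED measure is available".

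**Endpoints sent there.** Tables GPHZ.4.2, 4.3 and 4.11 send hepatic fat fraction (HFF), VAT/SAT, SF-36v2, IWQOL-Lite-CT and EQ-5D-5L to the ANCOVA of 4.4.2.1, on the Efficacy Analysis Set (EAS). The row "Proportion of participants who achieved improvements of NAFLD" in Table GPHZ.4.2 points instead to 4.3.2.2.

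**Which ED values count.** Under SAP section 3 the EAS stops at last dose plus 7 days, or plus 14 days for imaging. The Schedule of Activities (Protocol 1.3, Table 3) allows ED imaging only after at least 36 weeks on drug. ED questionnaires have no such minimum.

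**Protocol method.** Protocol 9.4.3.2 planned MMRM for other continuous efficacy endpoints. SAP 4.9 lists no change on this point.

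**The concern.** LOCF enters the participant's state at stopping as if it were the Week 72 state. The hypothetical estimand asks for the Week 72 state had treatment continued. The two agree only if the value would not have changed between stopping and Week 72.

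The gap matters most for PROs. A participant who stops during the 20-week escalation and completes the ED questionnaires within 7 days of the last dose contributes that score as a Week 72 score. Repeated measures in the same tables go through MMRM, so one declared estimand is analysed under two different missing-data assumptions.

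At stake is what the Week 72 differences in physical function, health status, liver fat and visceral fat mean. The rule also stands in SAP 4.1 beside a sentence that sends all secondary Week 72 missing values elsewhere.

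**Working it through.** **1. The plan's own figure.** The only stated power is for the co-primary endpoints: more than 90% per dose (SAP section 5). Inputs are 87 × 0.75 ≈ 65 per arm, difference 11, SD 10 and two-sided alpha 0.025. The SE is 10 × √(2/65) = 1.754, and 11/1.754 = 6.27. Power is Φ(6.27 − 2.24) ≈ 99.997%, so the figure holds. The SAP gives no effect, SD or power for PROs, HFF or VAT/SAT; everything below rests on assumptions.

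**2. Formula for LOCF.** Let d be dropout, q the share of dropouts with a usable ED value, and f the share of the Week 72 effect already present at ED. With flat placebo and equal dropout:

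- weight of carried values: w = qd / ((1 − d) + qd)
- LOCF effect / true effect = 1 − w(1 − f)

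The plan assumes d = 0.25. Then w = 0.25 at q = 1, and w = 0.125/0.875 = 0.143 at q = 0.5.

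| f | q = 1 | q = 0.5 |
|---|---|---|
| 0.25 | 0.81 | 0.89 |
| 0.50 | 0.875 | 0.93 |
| 0.75 | 0.94 | 0.96 |
| 1.00 | 1.00 | 1.00 |
| 1.20 | 1.05 | 1.03 |

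The f = 0.25 row is a corner case in which every dropout leaves with a quarter of the effect in place.

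**3. Averaging over dropout times.** A simulation used 4,000 trials per scenario, 87 per arm, a true effect of 0.50 SD, dropout uniform over weeks 4 to 72 and flat placebo. Monte Carlo error is about 0.002 to 0.003.

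| Assumed course of the drug effect | PRO type: ED at any time | Imaging type: ED at 36 weeks or later |
|---|---|---|
| Linear to Week 72 | 0.442 | 0.479 |
| Exponential, time constant 20 weeks | 0.474 | 0.499 |
| Plateau at Week 36 | 0.476 | 0.501 |
| Peak at Week 36, then waning | 0.485 | 0.508 |

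Against 0.50, the PRO loss runs from 3% (0.015/0.50) to 12% (0.058/0.50). For imaging it runs from a 4% loss (0.021/0.50) to a gain of about 2%. ANCOVA on observed Week 72 values gave 0.497 to 0.505 throughout.

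Hand check, linear PRO case: mean f = ((4 + 72)/2)/72 = 0.528; 1 − 0.25 × 0.472 = 0.882; × 0.50 = 0.441, against 0.442 simulated.

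**4. The sign can reverse.** Suppose the drug arm is at its Week 72 level by ED, placebo reaches 0.3 of the drug–placebo effect by Week 72 and is at half of that at ED, with 25% dropout in both arms. The drug mean is 1.3. The placebo mean is 0.75 × 0.3 + 0.25 × 0.15 = 0.2625. The difference is 1.04 against a true 1.00. With 15% versus 35% dropout (drug versus placebo), drug at 0.9 of its change at ED, and placebo reaching 0.5 but at 0.3 of that at ED: (0.85 × 1.5 + 0.15 × 1.35) − (0.65 × 0.5 + 0.35 × 0.15) = 1.4775 − 0.3775 = 1.10. A simulation with the drug arm plateauing at Week 36, placebo still improving and 15% versus 35% dropout gave 0.513 for both endpoint types.

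**5. The NAFLD cross-reference.** The imputation in SAP 4.3.2.2 takes predicted body weight from the repeated-measures model and dichotomises it. HFF has one scheduled post-baseline scan (Visit 21), so no such model of HFF exists.

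**The case against.** The defence has real points.

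- **LOCF is an explicit exception.** SAP 4.1 itself carves out single-post-baseline measures, and 4.4.2.1 and 4.4.2.2 repeat it. A programmer would probably run LOCF. This stands: the clash in 4.1 is loose drafting to tidy, and the NAFLD pointer is probably a mis-reference for 4.4.2.2.
- **The reach is limited.** The 7-day limit removes late ED scores. The 36-week rule keeps early scans out. Both stand and are reflected above.
- **The controlled hypotheses are untouched.** Only secondary and exploratory endpoints are affected, outside the multiplicity-controlled tests. This also stands.

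A reader might infer more than the documents support:

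- **That LOCF biases these effects toward the null.** This needs a drug–placebo gap still growing at ED. The documents give no time course, and step 4 shows the opposite sign.
- **That ED scores on drug are depressed by intolerance.** An assumed 3-point drop against a 5-point effect gives 22 to 23% attenuation, but neither figure has a source in the documents.
- **That the intervals under-cover in their own right.** In a similar simulation of 3,000 trials the model SE was 0.99 to 1.03 times the empirical SD, so any coverage loss came from bias. At effect 5, SD 9 and all ED scores usable, coverage was 93.5 to 94.4%.
- **That LOCF removes participants with under 36 weeks' exposure from the imaging analyses.** The protocol's ED schedule does that.

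None of this makes the carried-forward value an estimate of the stated target.

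**Conclusion.** The mismatch between estimand and analysis holds and can be read directly from the documents. PROs are the main concern; for HFF and VAT/SAT the practical effect is small. The ranges in step 3 (roughly 3 to 12% attenuation for PROs, about 0 to 4% for imaging) rest on the plan's 25% dropout plus assumed effect courses, flat placebo, uniform dropout times and every eligible ED value being usable. Fewer usable ED scores shrink the PRO figure. Continuing placebo change or higher placebo dropout can turn the bias away from the null. The documents do not settle which case applies, and that is itself a reason not to make LOCF the main analysis. This should be corrected, but it does not threaten the trial's primary conclusion.

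**What to change.** 1. In SAP 4.1, 4.4.2.1 and 4.4.2.2, make the main analysis of single-post-baseline endpoints one of two options. The first is ANCOVA or logistic regression on observed Week 72 EAS data, which is what MMRM reduces to for a continuous measure with one post-baseline visit. The second is multiple imputation under missing at random within arm, using baseline value, strata and on-drug body-weight visits, combined by Rubin's rules. The second is better if dropout depends on the weight course.
2. Leave the ED value out of the imputation model. PROs are taken only at Visits 3, 21 and ED, so nobody in the EAS has both an ED value and an on-drug Week 72 value, and their relation cannot be estimated.
3. Keep LOCF as a sensitivity analysis.
4. Reword SAP 4.1 so that one rule governs these endpoints.
5. In Table GPHZ.4.2, point NAFLD improvement to 4.4.2.2 under the same rule.
6. List the departure from Protocol 9.4.3.2 in SAP 4.9, with its justification.

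**Cost:** SAP wording, a little programming and somewhat wider intervals. Relative to LOCF, observed-data intervals for PROs widen by about √(1/0.75) = 1.15 times if every dropout had a usable ED score, and √(0.875/0.75) = 1.08 times if half did. In the step 3 simulations, rejection rates at the 5% level for PROs were 0.90 to 0.91 on observed data, against 0.92 to 0.96 with LOCF.
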